CTC uses the Information-Motivation-Behavioral skills (IMB) model^{3,4} to achieve changes among active PWID through seven short modules. Information and motivational domains are addressed in guided conversations about (1) their own first injection episode and consequences, (2) past experiences initiating injection-naive people and consequences, (3) health, legal, and social risks related to injection drugs, (4) health, legal, social risks of initiating people, and (5) identifying their own behaviors that might promote injection among others. The behavioral skills domain is addressed through a (6) skill-building discussion and rehearsal of responses to possible initiation scenarios, and (7) safer injection education. CTC pilot study results found significant reductions in injection initiation episodes; however, the study did not have a control group.⁷ Our specific aims are:

Aim 1: To test the efficacy of CTC on reducing the number of non-injectors initiated into injection (counts) by PWID. *Hypothesis 1*: PWID who receive CTC will report initiating fewer non-injectors into drug injection at 6 and 12 months as compared with PWID in the equal attention control condition.

Aim 2: To test the efficacy of CTC on reducing the number of times PWID are asked to initiate (counts) someone into injection. Hypothesis 2: PWID who receive CTC will report having been asked fewer times to initiate someone into drug injection at 6 and 12 months as compared with PWID in the equal attention control condition.

Aim 3: To test whether injection initiation social learning risks (injecting in front of, describing injection to, and speaking positively about injection to non-injectors) act as mediational mechanisms for the efficacy of the CTC intervention on initiation and request-to-initiate outcomes. Hypothesis 3: Social learning variables will significantly mediate the association between the CTC intervention and episodes of initiating and being requested to initiate someone into drug injection at 6 and 12 months.

Following completion of 12-month follow-up interviews, we will collect elucidation interviews with up to 100 PWID for purposes of providing preliminary data on key issues related to 1) Hepatitis A and C risk, needs, and services collected through a quantitative survey, and 2) experiences with drug effects and withdrawal and symptoms management in a qualitative audio-recorded interview.

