3.15. Data collection measures. Data collection measures were selected based on their relevance to evaluating CTC, applicability to social learning theory and IMB model, and potential as confounders. Items from each area are described below and a draft of the baseline questionnaire is included in **Appendix H**.

3.16. Main outcome measures for **Aims 1 & 3** will be the number of people initiated in the past 6 months. This item will be assessed by asking the following questions: "In the past 6 months, have you helped someone get their first hit (the first time they ever injected)?" If participants respond Yes, they will be asked the following question: "How many people (total) have you helped get their first hit (inject for the first time) in the past 6 months?" Not applicable responses (or No on the first item) will be recoded as zeros for data analysis purposes. For **Aims 2 & 3** we will ask the following items: "In the past 6 months, have you been asked to help someone inject an illicit drug for the first time?" Participants responding 'yes', were then asked how many people had asked them to provide their first injection. The time frame of 6 months allows us to assess changes in the outcome at 6 months (as was done in the pilot) and 12 months. The use of a count approach for outcome variables enables us to account for changes even if they only occur among high volume initiators and those with multiple injection initiation social learning risk. We will also collect data on sex risk, specifically, unprotected sex, multiple sex partners, and sex risk by partner type^{91,92} for purposes of determining the efficacy of the attention control condition although this is not an aim of the proposed study.

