3.17. Main independent measures will be intervention condition: CTC or equal attention control group for Aims 1 & 2. For Aim 3, we will also evaluate three injection initiation social learning risks as mediating variables. These items are intended to capture social learning constructs (i.e., observation of behavior, supportive interactions, and reinforcement) within the social processes of injection initiation. To capture observing, we will ask current PWID the following item: "In the past 6 months, have you injected drugs in front of someone who has never injected an illicit drug?" To capture interaction, we will ask "In the past 6 months have you explained or described how to inject to someone who has never injected an illicit drug (i.e., a noninjector)?" To measure reinforcement we will ask, "In the past 6 months, have you spoken positively about injecting with someone who has never injected an illicit drug?" Each item is a binary variable (Yes/No) where Yes denotes endorsing the injection initiation social learning risk assessed.

We will also collect IMB constructs related to injection initiation and sex risk. For the information construct, we will collect true or false knowledge items on sex-related HIV prevention provided by Kalichman, Simbayi and others^{5,6} and develop similar items for injection initiation risks. To develop injection initiation risk motivation and behavioral skill items we will follow procedures outlined by Kalichman, Simbayi and others.^{5,6} For sex-risk related motivation and behavioral skill items we will draw from existing studies.^{5,6} All injection initiation risk and sex-related IMB skill items will all be pilot tested. Psychometric properties of existing measures are known and acceptable, however, we will test both existing and new measures for their applicability to this study population. Drafts of all items are provided in the baseline survey (**Appendix H**).

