Aim 3: To test whether injection initiation social learning risks (injecting in front of, describing injection to, and speaking positively about injection to non-injectors) act as mediational mechanisms for the efficacy of the CTC intervention on initiation and request-to-initiate outcomes. H3: Social learning variables will significantly mediate the association between the CTC intervention and episodes of initiating and being requested to initiate someone into drug injection at 6 and 12 months. The outcome variable will remain counts of the number of episodes initiating someone into drug injection (Aim 1) and the counts of request to initiate another person (Aim 2). The mediational models will be specified following the work of Baron and Kenny and newer generalizations.¹⁰⁶⁻¹⁰⁸ With only three time points, we can examine the effect of baseline randomization to treatment status on 12-month counts of injection initiation as the outcome and 6-month injection-risk behavior variables as the mediators. The lagged approach can be used as static measures at 6 months and 12 months, or changes in injection initiation social learning risks and IMB skills constructs that precede changes in the number of counts of initiation as outcome. This latter approach is strong in that the change in a variable, created by difference scores, is isolated so that it precedes the subsequent outcome.

There are also techniques for estimating mediational models with only 2 time-points;¹⁰⁹ consequently, we will examine mediation from randomization to 6-month follow-up with the mediator and outcome measured concurrently. We can estimate separate mediational models for each injection initiation social learning risk and IMB skills construct, or enter the mediation mechanisms together into a single model, while examining overfit due to multiple mediational paths.¹¹⁰ Omnibus measures of model fit (chi-square, root mean square error of approximation, Tucker Lewis Index [TLI]), and specific path coefficients will be used to assess the treatment effect and test for the mediational pathways. The null hypothesis will be rejected if the p value for the variable that denotes treatment condition is below 0.05. Proposed Co-I [name] has extensive experience with these techniques as part of longitudinal community-based interventions.^{105,111,112}

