accounting for attrition, a final study of 800 participants at the 12month follow-up, evenly randomized, will have excellent power to detect small (0.82), moderate (0.88), and large (0.99) effect sizes. We also examined power for our mediational analyses in which the injection initiation risk variables will be differentially associated with treatment assignment. Following data from Co-I [name] for the mediational models, we expect that there was a 37% change in transition from initiation to non-initiation, and a 38% reduction in the participants injecting in front of injectionnaive people. These parameter estimates were converted to a Monte-Carlo simulation in Mplus, and we will have power to detect a mediational effect of for moderate to large pathways (Tx \rightarrow Mediator \rightarrow Outcome). Note that we will not have sufficient power for small mediational effects with our proposed sample, which may be clinically insignificant anyway.

1000

1500

High

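### The only thresholded rejection rule in the Aim 3 analysis uses the treatment variable's p-value, which does not test the indirect effect that H3 claims

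*Combined protocol and SAP*

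**What the plan says.** Section 1.0 states the hypothesis: "Social learning variables will significantly mediate the association between the CTC intervention and episodes of initiating", with requests to initiate as a second outcome, at 6 and 12 months. The three social learning mediators are yes/no items (section 3.17).

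In section 13.1 the Aim 3 text cites a mediation framework and later generalizations of it, without choosing one. It allows separate or joint mediator models, and static or change scores. It describes a lagged analysis (6-month mediator, 12-month count) and a second one: "we will examine mediation from randomization to 6-month follow-up with the mediator and outcome measured concurrently". After naming overall fit measures, it says that "specific path coefficients will be used to assess the treatment effect and test for the mediational pathways". The next sentence is the rule: "The null hypothesis will be rejected if the p value for the variable that denotes treatment condition is below 0.05".

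Section 13.2 claims that "we will have power to detect a mediational effect of for moderate to large pathways", with no numerical power and no named test. Its mediator input is "a 38% reduction in the participants injecting in front of injectionnaive people". Section 7.1 describes Aim 3 as exploring the mechanism, whereas sections 1.0 and 13.1 say it will be tested.

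**The concern.** An indirect effect has two legs: treatment must change the mediator, and the mediator must change the count. The plan does not say which treatment coefficient its rule refers to. There are four readings.

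1. **Outcome model with the mediator.** The coefficient is the direct effect, the part that is not mediated.
2. **Outcome model without the mediator.** It is the total effect, whatever the route.
3. **Mediator model.** It is the first leg only, and says nothing about whether the mediator affects the count.
4. **A rule meant for H1 and H2.** The Aim 1 and Aim 2 text gives no rejection rule, so this is plausible. Aim 3 then has no decision criterion.

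Readings 1 to 3 can each declare mediation where there is none. Reading 1 also misses complete mediation, and reading 2 often does; reading 3 does not. Under reading 4, with two outcomes, three social learning mediators, further IMB constructs and several model forms left open, a mediation claim could be settled after the results are seen. Section 13.1 blinds the analysts to prevent that kind of choice.

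**Working it through.** **The plan's own figure.** Section 13.2 gives no numerical mediation power, so there is none to reproduce. Its event-rate input does reproduce: 431/809 × 1,076 = 573.2 (stated 573).

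**Inputs from the plan**
- Analysed sample: 1,076 × 0.75 = 807, stated as about 800, so 400 per arm.
- Control mean per 6 months: 573/1,076/2 = 0.266.
- Mediator reduction: 38%.
- Direct rate ratio where a direct effect exists: 0.5, the halving expected in section 13.2.

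**Assumed, because the plan does not give them**
- Control mediator prevalence *p*: 0.3, 0.5, 0.7.
- Mediator-outcome rate ratio *R*: 2, 3, 5, 10.
- Negative-binomial *k*: 0.3, 1.0.

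This makes 3 × 4 × 2 = 24 settings.

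**Method.** Poisson regression with sandwich standard errors, 2,000 trials per setting (1,000 in the third scenario). The two-path test requires both treatment-to-mediator and mediator-to-count to have p < 0.05.

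| True state | Direct effect (1) | Total effect (2) | Treatment to mediator (3) | Two-path test |
|---|---|---|---|---|
| Complete mediation, mediator down 38% | 4.8–6.3% | 7.5–57.6% | 96.2–100% | 85.1–100% |
| No mediation, mediator equal in both arms, direct rate ratio 0.5 | 77.6–98.0% | 74.8–97.9% | – | 4.0–6.1% |
| Mediator shifts but does not affect the count | – | – | 96.5–100% | 4.4–5.8% |

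**Why the total effect is weak in the first row.** Under complete mediation through one mediator, the overall rate ratio is

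[1 + 0.62*p*(*R* − 1)] / [1 + *p*(*R* − 1)].

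- *p* = 0.3, *R* = 2: 1.186/1.3 = 0.91.
- *p* = 0.7, *R* = 10: 4.906/7.3 = 0.67.
- As *R* grows, the limit is 0.62.

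A 38% drop in one mediator therefore cannot by itself produce a halving. A halving needs, for example, a 60% drop with *R* = 11 at *p* = 0.5: (1 + 0.2 × 10)/(1 + 0.5 × 10) = 3/6 = 0.5. In that case the total effect rejects in 75.8–90.4%, the direct effect in 5.7–6.6% and the two-path test in 100%.

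**Checks under other models**
- *Plain Poisson counts*, *p* = 0.5, 1,000 trials. With no treatment effect on the mediator and a direct rate ratio of 0.5, the total and direct effects each reject in 99.5% and the two-path test in 4.3%. Under complete mediation with *R* = 3 or 2, the total effect rejects in 35.1% or 18.0%, the direct effect in 5.1% or 4.4%, and the two-path test in 100% or 99.9%.
- *Binary part of a two-part model* (assumed 12% initiating, mediator odds ratio 5, direct odds ratio 0.45; 1,500 trials). The direct effect rejects in 4.5–5.9% under complete mediation and 85.9–88.7% under none. The two-path test rejects in 97.0–100% and 4.9–5.0%.
- *Smaller direct effects, no mediation* (six settings, 600 trials each). The treatment-variable rule rejects in 30–55% at a direct rate ratio of 0.7, 16–28% at 0.8 and 7–11% at 0.9.

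**The case against.** The strongest reply is that the sentence was never meant for H3. The sentence before it names two tasks, assessing the treatment effect and testing the pathways, and the rule fits the first. H1 and H2 have no other rule. On that reading no wrong test is applied to H3, and the error rates above describe a procedure that may never be run. This may well be what the authors intended, but the rule stands in the Aim 3 text without that limit, and accepting the reply leaves H3 with no criterion. The correction is the same.

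A path test at 0.05 may also be implied by the cited framework, the reference to path coefficients and the two-sided alpha in section 13.2. That alpha is a power input, and none of the three says when an indirect effect counts as shown.

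The size does depend on assumptions. False-declaration rates near 80–98% need a direct rate ratio of 0.5, which comes from an uncontrolled pilot; they fall as the effect weakens but stay above 5%. The total-effect reading does better if mediation is strong enough to halve the count. The simulations are single-equation models, not the planned two-part SEM, of which only the binary part was checked.

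Finally, Aim 3 is described once as exploratory. But it is also stated as a hypothesis of significant mediation, and section 13.2 sizes the trial for all three hypotheses.

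**Conclusion.** The concern holds. The one thresholded rule in the Aim 3 analysis does not test H3 under any reading, and no criterion for the indirect effect is written elsewhere. This follows from what the coefficients mean and does not depend on the simulation.

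The direct-effect reading comes close to inverting the answer: it usually declares mediation when a halving is wholly unmediated, and rejects at about the nominal 5% when mediation is complete. The exact rates depend on the assumed mediator prevalence, rate ratio and overdispersion, and on the size of the direct effect.

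This should be fixed but is not fatal. Aim 1 and 2 efficacy conclusions are untouched, and because mediators and outcomes are collected at baseline, 6 and 12 months, Aim 3 remains answerable.

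**What to change.** Limit the p < 0.05 sentence to H1 and H2. For H3, add wording such as:

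> Mediation is concluded for a mediator-outcome pair if the 95% bootstrap confidence interval for the indirect effect (treatment to mediator to count, adjusted for baseline mediator and outcome) excludes zero.

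Then specify:
- **Primary model.** Apply the criterion to the lagged model, 6-month mediator and 12-month count.
- **Concurrent 6-month model.** If it is kept because H3 covers 6 months, use the same criterion and report that it cannot establish temporal order. Both items look back over the same period: "In the past 6 months, have you injected drugs in front of someone who has never injected an illicit drug" and "In the past 6 months, have you helped someone get their first hit".
- **Component.** Say whether the indirect effect is taken on the binary part, the count part or the overall mean of the two-part model.
- **Any or all.** State whether H3 needs one or all of the three mediators for each outcome. Three mediators and two outcomes make 3 × 2 = 6 pairs, so if any one suffices, say how error is controlled.

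The bootstrap criterion was tried with 600 trials and 400 resamples. It rejected in 98.8–100% under complete mediation, 4.3% under none, and 4.3–5.3% when the mediator shifted without affecting the count. A two-path test would also be defensible; what matters is that one criterion is fixed in advance.

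The cost is analysis-plan wording and computing time. No new data are needed.

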13.2. Sample size/ power analyses

Power calculations were estimated using Mplus by creating a Monte Carlo Simulation by generating a synthetic data set based on the expected parameter values, such as slopes, standard errors, and correlations among measured variables, for the anticipated treatment effect.^{113,114} Power was estimated assuming an intracluster correlation of 0.5, which is similar to our previous NIDA-funded studies.^{105,112,115} Statistical tests were two-sided, allowing detection of effects in either direction, and an alpha of .05 and power at 80%, corresponding to moderate effect sizes. Because the outcome is a count (i.e., Poisson), standard errors were estimated as non-normal via a sandwich estimator in Mplus.¹¹⁶ Co-Is [name] and [name] found that the number of participants who initiated people into injection was halved at follow-up.⁷ Preliminary data from MPIs [name] and [name]'s study in LA and SF indicated that 809 active PWID were found to have initiated 431 people in the past year. Using the same proportion, we expect that 573 people would be initiated by our proposed sample size of 1,076 participants at baseline (286 in each arm). If the number of people initiated by intervention group participants is halved, as suggested by [name] and [name]'s pilot data, that would represent a reduction of 143 people not being initiated into injection.

We also calculated the effect under different assumptions of attrition, subgroups (e.g., 25% Latino), sex, and age. For brevity, we illustrate power for primary outcome and most conservative—changes in the number of injection initiation events. We also account for 25% attrition—our worst-case scenario. To test the three hypotheses given our alpha and power specifications, we would need a baseline recruitment of 1,076 (n=538 per condition). We will recruit 1,076 participants to achieve the final sample of approximately 800 at the 12-month data point. The sample power for Cohen's effect sizes for small (2 percentage point difference), medium (5% difference) and large (10%–15% difference) effect sizes are plotted in **Figure 4**, revealing that after

accounting for attrition, a final study of 800 participants at the 12month follow-up, evenly randomized, will have excellent power to detect small (0.82), moderate (0.88), and large (0.99) effect sizes. We also examined power for our mediational analyses in which the injection initiation risk variables will be differentially associated with treatment assignment. Following data from Co-I [name] for the mediational models, we expect that there was a 37% change in transition from initiation to non-initiation, and a 38% reduction in the participants injecting in front of injectionnaive people. These parameter estimates were converted to a Monte-Carlo simulation in Mplus, and we will have power to detect a mediational effect of for moderate to large pathways (Tx \rightarrow Mediator \rightarrow Outcome). Note that we will not have sufficient power for small mediational effects with our proposed sample, which may be clinically insignificant anyway.

1000

1500

High

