2.0 OBJECTIVES AND PURPOSE

To achieve these aims, people who inject drugs (PWID) who report having initiated someone or having injection initiation social learning risks in the past 6 months (N=1,076) will be randomly assigned to receive CTC or an equal attention control condition in Los Angeles (LA) and San Francisco (SF), CA. Injection initiation

and injection initiation social learning variables will be collected at baseline, 6 months, and 12 months. CTC is brief, easy to implement, and novel in its focus on active PWID as a conduit for preventing injection initiation. If proven efficacious, CTC will be a much-needed, practical approach to preventing drug injection initiation.³⁹⁻⁴³

The main outcomes by Aim are as follows: 1) Counts of non-injectors initiated into drug injection at 6 and 12 months; 2) Counts of request to initiate a non-injector into drug injection at 6 and 12 months; and 3) Counts of noninjectors initiated into drug injection and request to initiate non-injectors at 6 and 12 months. The study will be implemented in 2 phases. Phase 1 involves adaptation and training of intervention personnel and Phase 2 involves implementing the full study.

Elucidation goals are to better understand issues related to 1) HAV/HCV effects and 2) drug effects and withdrawal and symptoms management PWID.

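### Section 13.2: the stated powers of 0.82 for a 2-point and 0.88 for a 5-point difference with 800 participants cannot both hold under one control rate

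*Combined protocol and SAP*

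**What the plan says.** Section 13.2 (Sample size/power analyses) reports power from a Monte Carlo simulation in Mplus. It describes two-sided tests with "an alpha of .05 and power at 80%, corresponding to moderate effect sizes", and adds: "Power was estimated assuming an intracluster correlation of 0.5". It allows for 25% attrition from 1,076 recruited, leaving about 800.

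The effect sizes carry Cohen's labels but are given as percentages: "small (2 percentage point difference), medium (5% difference", and large as 10% to 15%. For 800 participants split evenly, the plan "will have excellent power to detect small (0.82), moderate (0.88), and large (0.99) effect sizes".

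The same section gives a background rate: "809 active PWID were found to have initiated 431 people in the past year". From it the plan expects "573 people would be initiated by our proposed sample size of 1,076 participants at baseline (286 in each arm". The anticipated effect comes from the pilot, where "the number of participants who initiated people into injection was halved at follow-up". The section does not give a control-arm proportion of initiators, a mean number of people per initiator, or a dispersion. Section 3.16 defines the outcome as a count over the past 6 months.

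**The concern.** At a fixed sample size, a difference 2.5 times as large should have far more power unless the standard error also grows about 2.5-fold. Here power moves only from 0.82 to 0.88. The section also links 80% power to moderate effects and then reports more than 80% for small ones.

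The claim of excellent power for small effects is at stake. If it is unsupported, a null result could be read as ruling out a 2-point effect that the trial had little chance of detecting.

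**Working it through.** **Inputs (13.2).** 400 per arm; two-sided alpha 0.05; differences d of 0.02, 0.05 and 0.10 to 0.15; stated powers 0.82, 0.88 and 0.99; 431 people initiated by 809 PWID in a year; correlation 0.5.

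**Figures that reproduce.** 431/809 = 0.533. Then 0.5328 × 1,076 = 573.2, half of that is 286.6, and half again is 143.3. Attrition: 1,076 × 0.75 = 807. These are sound as 12-month totals for everyone randomised.

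**Formula.** Power = Φ(d/SE − 1.96), with SE = √{[p(1 − p) + (p − d)(1 − p + d)]·v/400}. Here p is the control proportion initiating. v = 1 is a single time point. v = 0.5 credits baseline and both follow-ups, reading the 0.5 as a within-person correlation: (1 + 0.5)/2 − 0.5² = 0.5.

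**1. Control rate that each stated power requires.**

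| Difference | Stated power | p needed, v = 1 | p needed, v = 0.5 |
|---|---|---|---|
| 2 points | 0.82 | 2.0% | 3.0% |
| 5 points | 0.88 | 7.9% | about 14% |
| 10 points | 0.99 | about 18% | about 38% |
| 15 points | 0.99 | essentially any | essentially any |

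At v = 1, a fall from 2% to 0% gives 0.815, so 0.82 sits at the extreme where nobody in the CTC arm initiates. A 5-point fall needs p of at least 5%. From p = 5% upward to 50%, power for 2 points is at most about 0.30 (0.53 with v = 0.5).

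**2. The same check without a control rate.** Power of 0.82 requires d/SE = 1.960 + 0.915 = 2.875, and 0.88 requires 1.960 + 1.175 = 3.135. The ratio is 1.09, for a difference 2.5 times as large. With equal standard errors, 0.88 at 5 points implies Φ(3.135 × 0.4 − 1.96) = 0.24 at 2 points.

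**3. Cohen's d reading.** d/SE = d × √(400/2) = 14.14d. For d = 0.2, 0.5 and 0.8, power is 0.81, 1.00 and 1.00. Only the first is near its stated value.

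**4. Secondary: the section's event rate.** This is a count, so a proportion needs an assumption.
- For 2% to 3% of PWID to account for 0.533 people each per year, initiators must average 0.533/0.02 = 27 down to 0.533/0.03 = 18 people a year.
- Assume half the annual count per window (0.266) and 1 to 5 people per initiator. Then p runs from 0.266/1 = 27% to 0.266/5 = 5%. Power for 2 points is 0.10 to 0.29 (v = 0.5: 0.15 to 0.50).
- Number per arm for 80% power: (1.960 + 0.842)² × [p(1 − p) + (p − d)(1 − p + d)] × v/d². At p = 5.3% this is 7.849 × 0.0826/0.0004, about 1,600. At p = 26.6% it is 7.849 × 0.381/0.0004, about 7,500. With v = 0.5 the range is about 800 to 3,700.

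**5. The anticipated halving.** With p = 0.266/k, d = p/2 and k people per initiator per window, power stays at 80% or more up to k of about 2.5 (4.7 with v = 0.5). At k = 5 it is 0.49 (0.78).

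**The case against.** The strongest reply is that the powers came from simulating a two-part zero-inflated Poisson latent growth model (13.1), which the plan says has more power than a raw difference. Its inputs are unlisted, and the figure that plots the powers cannot be seen in the text available for review. This stands as a limit: the approximations here are simpler than the planned model, and v = 0.5 is not an upper bound on what it could achieve. It does not explain why power barely rises between 2 and 5 points, since a more efficient model should help both.

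A second reply is that the sizes may be on another scale. The Cohen's d reading does give 0.81 for small, but it fails for the other two. Differences of 0.02 and 0.05 in the mean 6-month count, with Poisson variance around 0.266, give about 0.08 and 0.30.

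Third, a reader might infer that 431/809 by itself disproves the 0.82. The documents do not support that. The rate is a mean count, it is used only to illustrate expected totals, and nothing ties it to the simulation. Converting it to a proportion rests on the assumed people per initiator. Enrolment of those "who report having initiated someone or having injection initiation social learning risks in the past 6 months" may raise the proportion initiating, which would lower power for 2 points, but the plan does not say by how much.

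A reader might also conclude that all three powers conflict. The third need not: 0.99 at 15 points holds at almost any control rate.

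**Conclusion.** The concern holds for the first two stated powers. On a proportion scale, 0.82 at 2 points and 0.88 at 5 points need control rates of about 2% and 8% (3% and 14% with the variance halved), and the lower rates rule out a 5-point fall. The Cohen's d reading does not rescue them. The sentence linking 80% power to moderate effects conflicts with 0.82 for small ones.

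The mismatch with 431/809 is secondary. It rests on 1 to 5 people per initiator and an even split of the year into two windows.

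This does not show that the sample size is wrong or that the trial is underpowered for its anticipated halving. On the simple approximation, the halving keeps 80% power if initiators average up to about 2.5 people per window (4.7 with the variance halved), and falls below that beyond it. The documents do not say which case applies. Nor is there an error in 573, 286 and 143. Confidence is medium, because the simulation inputs are not given.

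**What to change.** In 13.2:
- State one control-arm proportion initiating per 6-month window, one mean count per initiator and one dispersion, and show that they are consistent with 431/809.
- Rerun the Mplus simulation of the planned two-part model with those inputs for all three effect sizes, and replace 0.82, 0.88 and 0.99 with the results.
- Say whether the sizes are absolute differences in proportion or Cohen's d.
- If the small effect is not reached, remove the claim of excellent power for it and give the smallest detectable difference.
- Reconcile the sentence linking 80% power to moderate effects with the reported values.
- Report power for the anticipated halving over the same inputs.

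The cost is one simulation rerun and some wording. No change in N is required, though the small-effect claim would probably be withdrawn.
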